## My View

|                                 |   |
|---------------------------------|---|
| Intervention Developer          | British Refugee Council   |
| Delivery Organisations          | British Refugee Council   |
| Evaluator                       | Ipsos MORI and Centre for Evidence and Implementation (CEI)   |
| Principal Investigator          | [name]   |
| Protocol Author(s)              | [name], [name], [name] (Ipsos MORI)
[name], [name] (CEI)  |
| Type of Trial                   | Non-blinded parallel two-armed randomised control trial with UASC individually randomised to a treatment or waitlist control group (on rolling basis) |
| Age or Status of Participants   | Unaccompanied Asylum Seeking Children (UASC) aged 12 to 18 (at the start of the intervention)   |
| Number of Participating Sites   | 5: 4 physical sites, 1 remote intervention site   |
| Number of Children and Families | 280   |
| Primary Outcome(s)              | Endline YP-CORE total score (difference in mean score, intervention vs control group)   |
| Secondary Outcome(s)            | Endline SWEMWBS (difference in mean score, intervention vs control group)   |
| Contextual Factors              |   |

## Summary

The My View therapeutic intervention for unaccompanied asylum seeking children (UASC) will be delivered by the British Refugee Council for 11 months between June 2021 and May 2022. It will be delivered by trained therapists in four physical (London, Kent, Birmingham, Leeds) locations and one therapist will operate remotely. In total, 280 UASC aged c. 12 to 18 at the start of the intervention will take part. My View contains either one to one therapeutic intervention over 12 one-hour long sessions (to be accessed by c. 190 young people), group therapy (to be accessed by c. 57 young people) or crisis intervention (to be accessed by c. 33 young people). The therapeutic interventions are supported by individual case work for each client, where relevant. For the purpose of the evaluation, the intervention period is 3 months.

The primary aim of the intervention is to improve the psychological and emotional wellbeing of UASC. The primary outcome measurement will be the YP-CORE, which will measure psychological distress at baseline and follow-up 3 months later. The secondary outcome measurement will be SWEMWBS, which will measure mental well being at the same time points as the YP-CORE.

The three elements of the evaluation are a randomised controlled trial, an implementation and process evaluation and a cost analysis. The evaluation will take place from June 2021 to June 2022.

## Background and Problem Statement

Unaccompanied Asylum Seeking Children (UASC) arriving in the UK often have complex psychological needs not only due to the trauma they are likely to have experienced, but also in relation to resettling in a foreign environment. Papadopoulos (2000b, 2001a,b) explains that:

[...] the ‘refugee trauma’ discourse tends to be restrictive because it emphasizes only one segment of the wide spectrum of the refugee experiences. This spectrum could be divided into at least four phases which have been identified as:

[figure not shown]
1. Anticipation: when people sense the impending danger and try to decide how best to avoid it;
2. Devastating events/adversity: this is the phase of actual violence, when the enemy attacks and destroys, and the refugees flee;
3. Survival: when refugees are safe from danger but live in temporary accommodation and uncertainty; and
4. Adjustment/Integration: when refugees try to adjust to a new life in the receiving country

Many UASC are said to fall through the gaps of existing CAMHS provision, or the provision provided lacks the necessary sensitivity to their circumstances. Davies Hayon and Oates’s 2019 literature review on the mental health service needs and experiences of unaccompanied asylum-seeking children in the UK identified high levels of needs. The review also highlighted barriers to using mental health services include lack of cultural awareness as well as young people’s mistrust and stigma and highlighted the importance of mental health services being available in spaces commonly used by UASC.

The British Refugee Council (BRC) has developed a programme to provide specialist therapeutic support to UASC, ‘My View’, as described in Figure 1.

Figure 1: Gap in provision filled by My View

### ‘My View’ specialist mental health support for separated children seeking asylum: context

Source: British Refugee Council presentation to WWCS, Ipsos MORI and CEI, 8 April 2021

 Davies Hayonm T. & Oates, J. (2019). The mental health service needs and experiences of unaccompanied asylum-seeking children in the UK: a literature review. *Mental Health Practice* 22(6), 13-20.

## Intervention and Theory of Change

### Background

The ‘My View’ intervention, provided by the British Refugee Council, is a specialist therapeutic service for separated young people and designed to fill the gap in mental health provision detailed above. It is a short-term intervention which aims to stabilise psychological/emotional wellbeing and better position clients to access longer-term interventions should it be needed via facilitated referrals to mainstream or longer-term specialist services.

The therapeutic care model has been tailored to meet the unique cultural and experiential needs of the client group, including being trauma-informed. Therapists employ creative/ play techniques and non-scriptocentric activities to ensure the service is accessible to non-English speaking clients. It also takes a holistic, biopsychosocial approach to considering client needs, recognizing that practical challenges with issues such as foster placements, housing and asylum claims will exacerbate mental health issues. The intervention involves one to one, crisis and group therapeutic interventions, with casework provided by the therapist as needed.

### Staff and staff training

The overarching model is the trauma-informed Refugee Council Therapeutic Model in providing holistic (psychosocial) therapeutic support. My View has a team of therapists from various disciplines and backgrounds. These include dramatherapy, play therapy, counselling, integrative therapy and art psychotherapy. Therapists use their skills and expertise in order to meet each individual client’s needs. All therapists are Health & Care Professions Council (HCPC) or British Association for Counselling and Psychotherapy (BACP) registered.

Before working with My View clients, all therapists receive five training sessions, with a total duration of 14 hours; the content is outlined in Table 1.

*Table 1: My view staff training schedule*

| Topic                                     | Audience   | Detail of session   |
|---|--|---|
| WWCSC: New Procedures – 3h         | Compulsory for everyone (staff and volunteers)                          | 
 
1. Introductions
 
2. External evaluation
 
3. Flowchart of activities and RCT
 
4. Evaluation and feedback
 
5. Targets
 
6. Focus on changes: referral procedure / times / waiting lists
 
7. Focus on changes: YP CORE
 
8. Focus on changes: contact with Evaluator and Funder
 
                                 |
| Therapeutic Care model – 3h        | Compulsory for everyone (staff and volunteers)                          | 
 
1. The Refugee Experience & Implications for Separated Children
 
2. Adolescence, Migration, Trauma: The intersection
 
3. Refugee Council Therapeutic model (Therapeutic relationship, Bearing witness, Psychoeducation)
 
4. Toolkit of interventions
 
5. Preventing burnout and self-care
 
                                       |
| In-Form Induction / refresher – 2h | Compulsory for new starters and open to everyone (staff and volunteers) | 
 
1. Recording of 1:1 (IA, other, final, DNA)
 
2. Recording of group session (first and other, DNA)
 
3. Recording workshop / outing
 
4. Recording group feedback / YP CORE
 
5. Recording communication with clients/stakeholders
 
6. Recording referral to external service
 
7. Change in client’s details (agencies)
 
 |

[figure not shown]
|   |  |   |
|---|--|---|
| Safeguarding Training – 3h                             | Compulsory for everyone (staff and volunteers)                          | 
 
1. Risk and classification of risk
 
2. Self-harm: assessment & management
 
3. Emergency management
 
4. Risk from others / risk to others
 
5. Procedures: respond – record, refer
 
6. Exploration of examples & case studies
 
                       |
| Admin & Life at the Refugee Council Induction – 3h | Compulsory for new starters and open to everyone (staff and volunteers) | 
 
1. Key processes (Team drive, Team folder, Team calendar)
 
2. Annual leave, toil and how to request
 
3. Expenses claim
 
4. Interpreter timesheets and Big Word
 
5. Client Data Spreadsheets & Weekly waiting lists
 
6. Other procedures & changes
 
 |

**Who (recipients): The target population and ultimate beneficiary of the programme**

The target population is Unaccompanied Asylum Seeking Children: those who have arrived in the UK alone without parents or guardians and are in the care of Local Authorities. The British Refugee Council supports young people regardless of the status of their asylum claim (not yet made, pending, granted). While new referrals must be 18 or under at time of referral, the Council will continue support for those who've had their 18th birthday.

The referral pathway is summarised in Figure 2:

Figure 2: Referral pathway

[figure not shown]
**What (procedures): the activities involved in delivery of the programme/intervention**

The intervention sees trained therapists working within the Refugee Council's trauma-informed therapeutic care model through the following interventions:

- A holistic initial assessment exploring the bio-psycho-social needs of the client as well as any practical issues that may be exacerbating their difficulties (e.g. asylum claims)
- Up to three crisis intervention sessions for young people with urgent needs (excluded from the evaluation)
- Up to 12 one-to-one counselling sessions with extensions in exceptional circumstances
- Group therapy sessions to build peer support networks and normalise their experiences e.g. dramatherapy, art therapy, music therapy
- Group psycho-educational workshops to help young people better understand mental health and the symptoms they may be experiencing such as flashbacks, disturbed sleep etc. (excluded from the evaluation)
- The Refugee Council also engages in informal clinical consultations with a young person's social worker and foster carer to establish informed onwards referrals pathways (i.e. casework)

The key activity flows are depicted in Figure 3:

Figure 3: My View activity flow

[figure not shown]
### Where (location): the delivery setting

The service is typically delivered face-to-face from one of the British Refugee Council

service hubs (London, Kent, Birmingham, Leeds), whether their own offices, outreach locations such as further education colleges and Reception Centres in Kent or through forums provided by other service providers (e.g. British Red Cross youth groups). However, during the Covid-19 crisis the service has moved to remote delivery with sessions held over the telephone and video calls, where engagement has continued to be high. One 'remote' intervention location will remain in place as part of the evaluation.

# Theory of change

Figure 4: My View Theory of Change

## Inputs

To deliver the intervention, the BRC received funding from WWCS and recruited 8 therapists (one to provide virtual therapy, one each in Leeds and Birmingham, two in Kent and three (accounting for 1.4 FTE) in London). Therapists receive 5 training sessions in the therapeutic method (as outlined in Table 1).

Clients are referred via internal or external pathways (e.g. Refugee Council Children's Advice Project, Youth Development Team, Red Cross, social services, KRAN) or can self-refer (see Figure 2 above).

## Activities

The young person's eligibility for the intervention is checked by a Refugee Council administrator. If eligible, the young person's details are entered into a Refugee Council database and an assessment of whether the young person is 'high risk' is carried out.

There are three ways in which therapists conduct direct work with clients:

**Crisis sessions.** Up to three of these are offered to clients with urgent immediate need for therapeutic support, classified as 'high risk'. If necessary, clients will be offered follow-on one to one therapeutic support. Therefore, they cannot be randomised as they will bypass the waitlist. Activities taking place in crisis intervention include stabilisation through grounding, explanation of symptoms, and drawing on internal strengths.

**Up to 12 one to one sessions,** or until there is a collaborative ending agreed before 12 sessions. These sessions last an hour each. The majority of clients will engage on a weekly basis, however may miss appointments throughout their intervention due to conflicting schedules (e.g. Home Office, college – beginning at college, termly timetable changes, social worker visits etc.), religious practices (e.g. Ramadan), sleep disturbances and other factors. This is why it takes longer than 12 weeks to complete the average intervention. For the purpose of the evaluation, a cut-off period of 3 months has been agreed to collect the follow-up measure. The structure and content of the 12 sessions is outlined in Table 2.

**Group sessions.** There is a minimum number of six (6) and maximum of 12 participants per group session. Group sessions are offered weekly, and attendance varies.

The format of general group sessions is as follows (and content outlines in Table 2):

- 'check-in' – gauging energy and mood levels,
- 'warm-up' activity to foster participation and engagement,
- 'main activity' – this can be a series of group exercises or one extended group activity,
- 'debrief' – to reflect or comment on activity and
- 'check-out' – to close and reflect on any take away learning etc.

The average length of engagement is 4.5 months. For the purpose of the evaluation, a cut-off point of 3 months has been agreed. We will randomise until January 2022, at which point the 'final' control group members will start receiving My View for 3 months (until April 2022).

In the summer months, the Refugee Council offers separate 'summer groups' which last 6 weeks. These groups tend to be activity focused, and operate on the basis of:

- intro to activity in session 1,
- sessions 2 to 5 engagement with activity and invitation for life/therapy connections to emerge and

- session 6 focusing on closure, reflections on takeaways and signposting to other services/1-2-1 therapy/ongoing open group.

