# Impact Evaluation

## Research Questions

In line with the logic model, we hypothesise that children and young people who take part in the My View intervention will have better psychological and emotional wellbeing. Our impact evaluation research questions are:

- What is the effectiveness of the My View intervention for UASC in terms of their psychological distress (as measured by Young Person’s Clinical Outcomes in Routine Evaluation (YP-CORE) measure), compared to a waitlist comparison group?
- What is the effectiveness of the My View intervention for UASC in terms of their mental wellbeing (as measured by the SWEMWBS), compared to a waitlist comparison group?

These questions are relevant for children and young people participating in either one-to-one therapy (over 12 sessions) or group therapy, or a mix of both. The comparison group will include young people who will wait three months before receiving the intervention. During this time, they will not receive any intervention delivered by BRC. However, it is possible that these individuals may receive support from elsewhere, which may vary.

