## Outcome Measures

### Primary outcome measure

The primary outcome measurement is the Young Person's Clinical Outcomes in Routine Evaluation (YP-CORE) measure. The YP-CORE is a measure of psychological distress and is widely used in mental health and school counselling services. It is freely available to use.

The baseline YP-CORE measurement will take place at the pre-assessment session for young people randomised i.e. both the treatment and control groups. Data will then be collected at the following timepoints:

- Treatment group:
  - Baseline at the pre-assessment session
  - After six My View sessions (midpoint)
  - After three months of My View (endline / post-treatment)
- Waitlist control group:
  - Baseline at the pre-assessment session
  - After three months of being on the waitlist (endline) – this will be at a second pre-assessment session before the young person starts My View
  - After six My View sessions (standard practice, not included in the evaluation)
  - After three months of My View (standard practice, not included in the evaluation).

---

 We have used 47 cases per block as an approximation to the 280 total required (i.e.  $47 \times 6 = 282$ ).

 <https://www.ncbi.nlm.nih.gov/pmc/articles/PMC6860299/>

 <https://www.corc.uk.net/outcome-experience-measures/core-measurement-tools/>

 If, for any reason, the midpoint questionnaire (after 6 sessions) gets delayed and therefore becomes close to the endline questionnaire (to be completed after three months), therapists may decide to only collect the endline.

The measure is brief, with just 10 items covering anxiety, depression, trauma, physical problems, functioning and risk to self. As such, this covers the following short-term outcomes included in the programme's theory of change:

- Psychological and emotional well-being
- Emotional self-regulation
- Safety and risk of harm

For each item, the respondent selects one response to indicate how they have been feeling over the last week:

- Not at all
- Only occasionally
- Sometimes
- Often
- Most or all of the time

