### **Young people in the control group (waitlist) will receive business as usual support**

Young people who are randomised to be on the waitlist will receive business as usual support. This support may vary depending on their location / local authority, the source of the referral and whether any other support can be provided. Due to the waitlist design, young people in the control group will be offered the intervention three months after the randomisation.

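### The protocol closes randomisation and starts the final waitlist controls on My View in the same month, January 2022, which cannot hold alongside a three-month wait counted from randomisation

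*Protocol*

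**What the plan says.** The only statement of when randomisation closes is in the Activities section, under group sessions: "We will randomise until January 2022, at which point the 'final' control group members will start receiving My View for 3 months". The sentence gives April 2022 as the end of those three months. Table 10 lists the first randomisation (week commencing 7 June) but no last one.

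The wait is described in three other places:

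- Impact Evaluation, Research Questions: "The comparison group will include young people who will wait three months before receiving the intervention".
- Ethics section on business-as-usual support for the waitlist: "young people in the control group will be offered the intervention three months after the randomisation". This counts the wait from randomisation.
- Primary outcome measure: the control endline falls after three months on the waitlist, and "this will be at a second pre-assessment session before the young person starts My View".

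The treatment-arm endline has a different anchor. Table 3 and the Missing Data section count three months from the start of the intervention. Table 10 ends RCT data collection in April 2022. The Summary says that My View "will be delivered by the British Refugee Council for 11 months between June 2021 and May 2022" and that the evaluation runs to June 2022.

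**The concern.** The Activities sentence puts two events in one month that the rest of the protocol separates by three. The control endline is half of the primary contrast, so whoever runs enrolment and the waitlist has to know which date governs.

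Each way of resolving the sentence has a different cost: controls without a full untreated endline, a smaller trial than the one in Table 4, or a data cut-off that falls too early for late treatment-arm endlines. The Analysis Plan expects control cross-over only through the override for high-risk cases, and the risk register adds attendance at drop-in groups. Neither foresees controls starting early because of a calendar date.

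**Working it through.** **Dates.** Inputs: randomisation closes and final controls start in January 2022 (Activities); wait of three months from randomisation (Research Questions, Ethics); endline at the end of the wait and before My View (Primary outcome measure).

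- January 2022 start minus 3 months = randomised by October 2021.
- January 2022 randomisation plus 3 months = endline and earliest start in April 2022.

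The two differ by three months, so the final controls cannot satisfy both.

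**The plan's own figure.** Inputs from Table 4 and its text: N = 280 (145 and 135, so P = 145/280 = 0.518), R² = 0.5, two-sided alpha 0.05, power 0.8, 6 strata.

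MDES = M × √[(1 − R²) / (P(1 − P)N)], where M = t(0.975) + t(0.80) on N − 6 − 1 − 1 = 272 degrees of freedom.

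This gives 0.238, which agrees with the stated 0.24. Power at 0.24 SD is 0.81. The MDES is not in error for 280.

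**Size under readings (a) and (b).** The protocol gives no accrual rate and no day in January, so I assume even accrual of 280 and vary the dates. Accrual starts on 7 June (first randomisation) or 15 June (mid-June start of RCT data collection) and ends on 1 or 31 January. The cut-off is three months before the January date.

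| Start | January date | Days to cut-off / all days | N by cut-off | MDES | Power at 0.24 | Controls after cut-off |
|---|---|---|---|---|---|---|
| 7 June | 31 Jan | 146/238 = 0.613 | 172 | 0.304 | 0.60 | 52 |
| 7 June | 1 Jan | 116/208 = 0.558 | 156 | 0.320 | 0.56 | 60 |
| 15 June | 31 Jan | 138/230 = 0.600 | 168 | 0.308 | 0.59 | 54 |
| 15 June | 1 Jan | 108/200 = 0.540 | 151 | 0.325 | 0.55 | 62 |

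N by cut-off is 280 × the fraction. Controls after cut-off is (280 − N) × 135/280; for the first row, 108 × 135/280 = 52.

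- **Reading (a)**, final controls start in January regardless of their wait: the last column counts those without a full three-month untreated endline, if the sentence is applied to everyone still waiting.
- **Reading (b)**, the January start is kept and the wait honoured: enrolment closes in October, and the N, MDES and power columns apply.

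**Reading (c)**, enrolment runs to January and the start date is misworded. Control endlines fall by April 2022, inside the data-collection period. Two other dates then come under strain:

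- *Treatment-arm endlines.* They count from the start of the intervention, so any gap between allocation and start moves them later. A young person randomised on 31 January who starts two weeks later has an endline in mid-May. As an illustration, take even accrual from 7 June to 31 January and a data close at the end of April. A one-week gap then affects about 7/238 × 145 = 4 treatment-arm members, and a two-week gap about 14/238 × 145 = 9. If randomisation stops on 1 January, a gap of that length loses none.
- *Delivery.* January + 3 months' wait + 3 months of My View = July 2022, past the May end of delivery and the June end of the evaluation. Counting back six months from the end of May 2022, the latest randomisation that fits both periods is the end of November 2021.

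**The case against.** A reader might infer that late controls must either lose their untreated endline or force an October close. The documents do not support that either/or. Under reading (c) January enrolment stands, control endlines fall in April within the Table 10 period, and the primary comparison is valid.

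A reader might also infer that all waiting controls are to be released in January. The Activities sentence speaks only of the final members, and it is descriptive text. The per-participant schedule under Primary outcome measure is clear, so a site would have to depart from three other statements for the control endline to be contaminated. The 52 to 62 controls show what a literal application would cost; they are not a forecast.

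The overrun of late controls' therapy past May does not bias the estimate. The protocol marks their measures after the wait as standard practice outside the evaluation, and the Ethics section promises an offer after three months, not completion by a given date. That conflict concerns delivery.

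Lastly, nothing links 280 to a particular enrolment window: the text says the sample size follows from delivery resources. The reduced sample sizes therefore hold only under the even-accrual assumption.

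All of this limits the consequences. It does not remove the conflict, because no other passage gives a last randomisation date or says which January event is misdated.

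**Conclusion.** The Activities sentence is wrong as written: the only stated rule for closing enrolment cannot be followed together with the control endline schedule. That conclusion is date arithmetic and needs no assumption.

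The consequence depends on what was meant. It ranges from an intact primary contrast with a data cut-off that is too tight (c), through a trial with power of roughly 0.55 to 0.60 at the stated effect (b), to more than a third of controls without a full untreated endline (a). The figures for (a) and (b) rest on even accrual and on the assumed start and January dates. The protocol does not show which date is mistaken, and the stated MDES of 0.24 is correct for 280.

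**What to change.** Reconcile the Activities sentence with the Summary, Research Questions, Primary outcome measure, the Ethics text on the waitlist, and Table 10. State one last-randomisation date. State also that each control's endline follows that person's own three-month wait and never the calendar close of randomisation.

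Then, depending on the date confirmed:

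- If enrolment to January is confirmed, extend RCT data collection in Table 10 into May 2022. Otherwise late treatment-arm endlines would be dropped as missing under the complete-case rule. The cost is a shorter analysis period before the June 2022 final report.
- If enrolment closes in October, restate the expected sample size and MDES, unless the sponsor can show that 280 is still reachable.

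When late controls begin My View is for the sponsor to reconcile across the Summary, Activities and Ethics sections; no rule is proposed here. Apart from any extension of data collection, the change is a few words of protocol text.
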